4.3.8 Pharmacodynamic Variables

The analysis of the PD data will be based on the PD population.

For cohort 5, if number of either Japanese subjects or non-Japanese subjects is less than 3, cohort 5 won't be included in "by ethnicity" analysis.

As secondary endpoints, individual subject pharmacodynamics data of serum concentrations of Immunoglobulin levels (total IgA, IgG and IgM) will be listed [Listings 16.2.6.3.1 (observed) and 16.2.6.3.2 (change from baseline)], observed and change from baseline will be summarized descriptively by treatment [Tables 14.2.7.1 (Immunoglobulin)] and by ethnicity and treatment [Tables 14.2.7.2 (Immunoglobulin)].

Individual subject circulating lymphocytes and lymphocyte subsets will be listed [Listings 16.2.6.4.1 (observed) and 16.2.6.4.2 (change from baseline), and 16.2.6.5.1 (observed) and 16.2.6.5.2 (change from baseline) respectively]; observed values and change from baseline will be summarized descriptively by treatment [Tables 14.2.8.1 (lymphocytes), and 14.2.9.1 (lymphocyte subsets), separately] and by ethnicity and treatment [Tables 14.2.8.2 (lymphocytes), and 14.2.9.2 (lymphocyte subsets), separately]. This assessment will be done for all lymphocytes, and also for lymphocyte subsets that are noted to show changes from baseline. These analyses will be conducted for cohorts 1-4 only.

Individual observed value, change from baseline and percent change from baseline plots against time (Figures [Total IgA: 14.2.2.1.1, 14.2.2.1.2 and 14.2.2.1.3], [Total IgG: 14.2.2.2.1, 14.2.2.2.2, and 14.2.2.2.3], [Total IgM: 14.2.2.3.1, 14.2.2.3.2 and 14.2.2.3.3]), and individual observed value, change from baseline plots against time (Figures [Lymphocytes (cohorts 1-4 only): 14.2.2.4.1 and 14.2.2.4.2], and [Lymphocyte subsets (cohorts 1-4 only): 14.2.2.5.1 and 14.2.2.5.2]) will be produced by treatment with each subject being identifiable. The actual sampling time will be used in days on the x-axis.

Mean (\pm SD), mean change from baseline and percent mean change from baseline plots against time (Figures [Total IgA: 14.2.2.1.4, 14.2.2.1.5 and 14.2.2.1.6], [Total IgG: 14.2.2.2.4, 14.2.2.2.5 and

PAREXEL International

Statistical Analysis Plan

14.2.2.2.6], [Total IgM: 14.2.2.3.4, 14.2.2.3.5 and 14.2.2.3.6]), and mean (\pm SD) and change from baseline plots against time (Figures [Lymphocytes (cohorts 1-4 only): 14.2.2.4.3 and 14.2.2.4.4] , and [Lymphocyte subsets (cohorts 1-4 only): 14.2.2.5.3 and 14.2.2.5.4]) will be presented by treatment; Mean(\pm SD), mean change from baseline and percent mean change from baseline plots against time by ethnicity and treatment (Figures [Total IgA: 14.2.2.1.7, 14.2.2.1.8 and 14.2.2.1.9], [Total IgG: 14.2.2.2.7, 14.2.2.2.8 and 14.2.2.2.9], [Total IgM: 14.2.2.3.7, 14.2.2.3.8 and 14.2.2.3.9]), and mean(\pm SD) and change from baseline plots against time by ethnicity and treatment (Figures [Lymphocytes(cohorts 1-4 only): 14.2.2.4.5 and 14.2.2.4.6] , and [Lymphocyte subsets (cohorts 1-4 only): 14.2.2.5.5 and 14.2.2.5.6]) will be presented as well. The nominal sampling time will be used in days on the x-axis. All treatments will be overlaid on the same plot. [REDACTED]

[REDACTED]

[REDACTED]

[REDACTED]

[REDACTED]

[REDACTED]

Following figures will be created:

- Figure 14.2.2.6.1: IgA subtype mean (\pm SD) over time by treatment
- Figure 14.2.2.6.2: IgA subtype mean (\pm SD) change from baseline over time by treatment
- Figure 14.2.2.6.3: IgA subtype mean (\pm SD) over time by ethnicity and treatment
- Figure 14.2.2.6.4: IgA subtype mean (\pm SD) change from baseline over time by ethnicity and treatment
- Figure 14.2.2.7.1: IgG subtype mean (\pm SD) over time by treatment
- Figure 14.2.2.7.2: IgG subtype mean (\pm SD) change from baseline over time by treatment
- Figure 14.2.2.7.3: IgG subtype mean (\pm SD) over time by ethnicity and treatment
- Figure 14.2.2.7.4: IgG subtype mean (\pm SD) change from baseline over time by ethnicity and treatment

PAREXEL International

Statistical Analysis Plan

Topic	Percentage
Smart homes	95
Smart cities	95
Smart transportation	95
Smart energy	95
Smart waste management	95
Smart agriculture	95
Smart healthcare	95
Smart water management	95
Smart manufacturing	95
The concept of a 'smart city'	60

If a baseline PD value is zero, then the percentage change from baseline will not be calculated. If a PD value is BLQ then the value will be set to the LLOQ. Similarly, for the PD plots, a BLQ value will be set equal to LLOQ.

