3.2.2.2. Pharmacodynamics Endpoints

- Changes in total serum IgG, IgA and IgM concentrations and time to recovery
- Changes in whole blood circulating lymphocyte populations

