8.9. Pharmacodynamics Analyses

Pharmacodynamic analysis will be performed using data from all subjects assigned to the PD Population.

PD for circulating lymphocyte, total IgA, IgG and IgM, and other relevant PD applicable markers in serum or appropriate matrix (using the raw data, change from baseline data and % change from baseline, as appropriate) will be summarized and plotted over time. Baseline data will be taken as the last measurement prior to dosing or average of the Screening and Baseline values, detail will be written in Statistical Analysis Plan.

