1.2 Secondary Objectives

- To characterize the pharmacokinetic (PK) profile of VIS649
- To evaluate the effect of ethnicity on the PK profile of a single intravenously (IV) administered dose of VIS649 in healthy Japanese and non-Japanese subjects
- To characterize the levels of anti-drug antibodies
- To characterize the effect of VIS649 on pharmacodynamic (PD) parameters including:
 - changes in serum total IgA, IgG and IgM concentrations and time to recovery.
 - changes in circulating lymphocyte populations in cohorts 1-4 only (this assessment will be done for all lymphocytes, and also for lymphocyte subsets that are noted to show changes from baseline)

PAREXEL International
Statistical Analysis Plan

- To assess ADA status impact on VIS649 PK parameters

■ [REDACTED]

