4.1.6 Pharmacodynamic (PD) Variables

Blood samples for PD parameters will be drawn in accordance with the Schedule of Assessments in Table 1.

Change from baseline will be calculated for each of following PD parameters:

- Immunoglobulin levels (total serum IgA, IgG and IgM)
- lymphocytes (and their subsets) for cohort 1-4
- Immunoglobulin subtypes (IgA and IgG), [REDACTED]
- [REDACTED]
[REDACTED]

Table 5 Immune Assessment B Cell Subsets, B

[REDACTED]
[REDACTED]
[REDACTED]
[REDACTED]
[REDACTED]

Immune Assessment B Cell Subsets, B

[REDACTED]
[REDACTED]
[REDACTED]
[REDACTED]
[REDACTED]

PAREXEL International
Statistical Analysis Plan

[REDACTED]

[REDACTED]

[REDACTED]

Table 6 Immunoglobulin Subtypes

IgA subtypes: [REDACTED]

IgG subtypes: [REDACTED]

And also time to recovery of total serum IgA, IgG and IgM will be analyzed, two measures will be used:

- 1) Time to return to normal range (for those parameters that fall below LLN).

[REDACTED]

[REDACTED]

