4.3.5 Interim Analysis

As participants in each dosing group complete their Week 16 visit, data clean-up and soft-lock will be performed for each cohort, in order to allow an interim assessment of PK, PD and safety data. PK/PD analysts will be permitted access to unblinded data, and to facilitate preparation of blinded data summaries for presentation to the Sponsor. The randomization code will be provided to the bioanalytical laboratories responsible for the analysis PK and PD endpoints. Following analysis of the

PAREXEL International

Statistical Analysis Plan

samples but prior to provision of the data to PAREXEL's statistician, the laboratory will re-code the data back to the corresponding original unique sample ID numbers, enabling differentiation but not identification of the subjects in order to maintain blinding integrity for the other assessments of the clinical study, until after database lock. The full randomization code will be broken only for purposes of data analysis and reporting or safety reasons. This will occur once all final data have been entered into the database and all data queries have been resolved, coding is complete, the assignment of subjects to the analysis sets has been completed and the database has been locked.

Interim summaries of PK, PD and safety data for selected or entire cohorts (inclusive of both VIS649 and placebo recipients, and therefore, still blinded) may be utilized for various reporting purposes prior to full database lock and unblinding if deemed appropriate.

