Table 14.2.6.2.2 Pharmacokinetic Parameters of VIS649 Descriptive Statistics by Overall Subject ADA Classification by Treatment and Ethnicity (Pharmacokinetic Population)

Pharmacodynamic Data

Table 14.2.7.1 Summary of Pharmacodynamic Parameters by Treatment : Immunoglobulin (Pharmacodynamic Population)

Table 14.2.7.2 Summary of Pharmacodynamic Parameters by Ethnicity and Treatment : Immunoglobulin (Pharmacodynamic Population)

Table 14.2.7.3 Summary of Pharmacodynamic Parameters by Treatment : Immunoglobulin Subtypes (Pharmacodynamic Population)

Table 14.2.7.4 Summary of Pharmacodynamic Parameters by Ethnicity and Treatment : Immunoglobulin Subtypes (Pharmacodynamic Population)

Table 14.2.7.5 Summary of Pharmacodynamic Parameter by Treatment: APRIL (Pharmacodynamic Population)

Table 14.2.7.6 Summary of Pharmacodynamic Parameter by Ethnicity and Treatment: APRIL (Pharmacodynamic Population)

Table 14.2.7.7 Summary of Pharmacodynamic Parameter by Treatment: a-g IgA (Pharmacodynamic Population)

PAREXEL International
Statistical Analysis Plan

Table 14.2.7.8 Summary of Pharmacodynamic Parameter by Ethnicity and Treatment: a-g IgA (Pharmacodynamic Population)

Table 14.2.8.1 Summary of Pharmacodynamic Parameters by Treatment : Lymphocytes (Pharmacodynamic Population)

Table 14.2.8.2 Summary of Pharmacodynamic Parameters by Ethnicity and Treatment : Lymphocytes (Pharmacodynamic Population)

Table 14.2.9.1 Summary of Pharmacodynamic Parameters by Treatment : Lymphocyte Subsets (Pharmacodynamic Population)

Table 14.2.9.2 Summary of Pharmacodynamic Parameters by Ethnicity and Treatment : Lymphocyte Subsets (Pharmacodynamic Population)

Safety Data

Adverse Events

Table 14.3.1.1 Overall Summary of Treatment Emergent Adverse Events (Safety Population)

Table 14.3.1.2 Treatment-Emergent Adverse Events by Treatment, System Organ Class and Preferred Term (Safety Population)

Table 14.3.1.3 Treatment-Emergent Adverse Events by Treatment, System Organ Class, Preferred Term and Maximum Severity (Safety Population)

Table 14.3.1.4 Treatment Emergent Adverse Events “Related to IMP” by System Organ Class, Preferred Term and Severity (Safety Population)

Table 14.3.1.5 Treatment Emergent Adverse Events “Not Related to IMP” by System Organ Class, Preferred Term and Severity (Safety Population)

Listing 14.3.2.1 All Serious Adverse Events (Safety Population)

Listing 14.3.2.2 Adverse Events Leading to Discontinuation (Safety Population)

Clinical Laboratory Tests

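### SAP 4.3.8 tabulates lymphocyte subsets without condition, then limits the assessment to subsets noted to change, so table content could depend on the result; no criterion is visible

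*SAP*

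**What the plan says.** SAP 4.3.8 (Pharmacodynamic Variables) plans subset tables by treatment: "observed values and change from baseline will be summarized descriptively by treatment [Tables 14.2.8.1 (lymphocytes), and 14.2.9.1 (lymphocyte subsets), separately". It plans Table 14.2.9.2 in the same way, by ethnicity and treatment. The output list in SAP Section 6 names the first table with no restriction: "Table 14.2.9.1 Summary of Pharmacodynamic Parameters by Treatment : Lymphocyte Subsets (Pharmacodynamic Population".

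The next sentence of 4.3.8 narrows the scope: "This assessment will be done for all lymphocytes, and also for lymphocyte subsets that are noted to show changes from baseline". The secondary objective in SAP 1.2 has the same clause, "also for lymphocyte subsets that are noted to show changes from baseline", and the endpoint definition in SAP 2.2.2 repeats it. The sentence that follows in 4.3.8 limits these analyses to cohorts 1-4.

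Two other parts of the SAP bear on the point. SAP 4.1.6 has change from baseline calculated for "lymphocytes (and their subsets) for cohort 1-4". The subset listings (16.2.6.5.1 and 16.2.6.5.2) and subset figures (14.2.2.5.1 to 14.2.2.5.6) are planned without the condition.

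**The concern.** Change from baseline is one of the two quantities that Tables 14.2.9.1 and 14.2.9.2 report. If a subset enters the tables because it changed, the tables are selected on their own outcome. Two things follow. The tabulated changes tend to look larger than they would across the whole panel. Subsets that did not change lose their tabulated by-dose and pooled-placebo values.

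The second consequence matters more here. Protocol 1.1 reports that lymphocyte populations in monkeys were not significantly affected. A reader who wants to know whether that holds in humans needs the numbers for the unchanged subsets as much as for the changed ones.

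There is also a practical problem. The SAP is meant to give programming specifications for the outputs, yet a programmer cannot tell from 4.3.8 which subsets belong in the two tables.

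**Working it through.** **Reading the text.** The documents give no figure to reproduce, so the main check sets the passages side by side.

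| Place in SAP | Subset output | Condition stated? |
|---|---|---|
| 4.3.8, listings | 16.2.6.5.1, 16.2.6.5.2 | No |
| 4.3.8, summaries | Tables 14.2.9.1, 14.2.9.2 | No |
| 4.3.8, next sentence | the assessment just described | Yes: subsets noted to change |
| 1.2 and 2.2.2 | secondary objective, endpoint | Yes, same clause |
| 4.3.8 and Section 7, figures | 14.2.2.5.1 to 14.2.2.5.6 | Cohorts 1-4 only (stated in 4.3.8); no selection on change |
| Section 6, table titles | 14.2.9.1, 14.2.9.2 | No |
| 4.1.6 | change from baseline calculated | Cohorts 1-4 only |

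The cohort limit that follows the clause in 4.3.8 plainly restricts the same outputs, so the natural reading is that the clause does too. No visible text gives a size, direction, visit, dose group, decision-maker or timing. By contrast, 4.3.8 sets a numerical rule for dropping cohort 5 from the by-ethnicity analyses (fewer than 3 subjects), and 4.3.9 names the sponsor as decision-maker for the optional PK/PD analysis.

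**Illustration of size.** The panel size is redacted and no test on subsets is planned, so every cut-off below is an assumption. Inputs from SAP Table 2: four dose groups (cohorts 1-4) with n = 7 on active drug in each. Assumptions: no true effect, independent groups, normally distributed changes, and a subset tabulated if any dose group passes a two-sided one-sample t cut-off (6 degrees of freedom).

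- Average absolute mean change without selection, in SDs of individual change: √(2/π)/√7 = 0.798/2.646 = 0.302.
- Share of unchanged subsets omitted, one visit: (1 − p)⁴.
- Inflation: average absolute mean change after selection, divided by 0.302, from 400,000 simulated sets.

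One visit:

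| Meaning of noted | Critical t | Unchanged subsets omitted | Inflation, flagged group | Inflation, all four groups shown |
|---|---|---|---|---|
| any change | 0 | 0% | 1.0 | 1.00 |
| p < 0.5 | 0.718 | 0.5⁴ = 6% | 1.6 | 1.04 |
| p < 0.2 | 1.440 | 0.8⁴ = 41% | 2.0 | 1.18 |
| p < 0.1 | 1.943 | 0.9⁴ = 66% | 2.3 | 1.28 |
| p < 0.05 | 2.447 | 0.95⁴ = 81% | 2.5 | 1.35 |

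The lymphocyte row of SAP Table 1 appears to show Weeks 4 and 16, plus optional Weeks 20 and 24, although the table extraction is imperfect. With an assumed correlation of 0.5 between visit changes, and a subset tabulated if any visit in any dose group passes:

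| Cut-off | Omitted, 2 visits | Omitted, 4 visits | Inflation over all cells shown, 2 visits | Inflation over all cells shown, 4 visits |
|---|---|---|---|---|
| p < 0.5 | about 1% | 0% | 1.00 | 1.00 |
| p < 0.2 | 19% | 6% | 1.07 | 1.02 |
| p < 0.1 | 46% | 25% | 1.14 | 1.06 |
| p < 0.05 | 68% | 49% | 1.19 | 1.11 |

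These figures show the direction of the effect and how much the undefined wording leaves open. They are not estimates for this trial.

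**The case against.** The strongest reply is that little is lost. Figures 14.2.2.5.3 and 14.2.2.5.4 plot subset means and mean changes by treatment, Figures 14.2.2.5.5 and 14.2.2.5.6 do so by ethnicity and treatment, and Figures 14.2.2.5.1 and 14.2.2.5.2 show individuals. The figure text repeats the cohort limit but not the selection clause, and the listings are unconditional. Unchanged subsets would therefore still be reported graphically and individually. This stands. What could be missing is the numerical table.

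A second reply is that, in continuous data, almost any subset shows some change, so the clause may exclude nothing. That reading is possible and corresponds to the first row of the one-visit table. The SAP does not say that it is the one intended.

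A reader might also infer more than the documents support:

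- **That no criterion exists.** Parts of 4.1.6 and 4.3.8 are redacted, so only the absence of a visible criterion can be claimed.
- **That subsets will be picked with treatment known.** SAP 4.3.5 says "PK/PD analysts will be permitted access to unblinded data", but for interim work and to prepare blinded summaries. Nothing gives those analysts the choice of subsets.
- **That the SAP departs from its protocol.** The supplied protocol states the endpoint as "Changes in whole blood circulating lymphocyte populations", and its section 8.9 summarises "PD for circulating lymphocyte, total IgA, IgG and IgM, and other relevant PD applicable markers in serum or appropriate matrix", both without the clause. However, the SAP follows Amendment 2, Version 3.0, and the supplied protocol appears to be an earlier version: its fifth cohort is optional and it has no vaccine. The comparison is not evidence of a departure.
- **That results are inflated 2.5 times.** That figure applies only to a flagged dose group at the strictest assumed cut-off.

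**Conclusion.** The point holds as an internal inconsistency. SAP 4.3.8 plans the subset tables without condition and then, on the natural reading, permits the tabulated subsets to be chosen by the change they report. It does not show that subset results would be concealed or that any inference would be invalid. The summaries are descriptive with no test attached, total lymphocytes are tabulated in any case, and the listings and figures cover the subsets without the condition.

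The size of any selection effect is unknown. In the illustration, the share of unchanged subsets left out of the tables runs from 0% to 81% with one visit and from 0% to 49% with four. That range rests wholly on assumed cut-offs, no true effect, and the independence and correlation assumptions stated above. The inconsistency stands within the SAP alone and does not depend on the protocol comparison. It should be corrected because it is easy to remove and concerns a stated secondary endpoint.

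**What to change.** Delete the conditional sentence in SAP 4.3.8. State instead that every assayed lymphocyte subset is summarised, observed and change from baseline, for each cohort 1-4 dose and pooled placebo at all collected visits in Tables 14.2.9.1 and 14.2.9.2, with the by-ethnicity split in the latter. The tables then match the listings and Figures 14.2.2.5.1 to 14.2.2.5.6. Label any highlighting of particular subsets in the report as post hoc.

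Align SAP 1.2 and 2.2.2 after checking the wording in the protocol version that the SAP cites (Amendment 2, Version 3.0). If the clause comes from there, tabulating every subset still covers what it asks for.

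The cost is a change of SAP wording and longer tables. No new data are needed, because change from baseline is already to be calculated for the subsets.

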4.3.9 Pharmacokinetic/Pharmacodynamic Analysis

An exploratory PK/PD analysis between the serum concentrations of the study drug and PD assessments may be performed, if deemed appropriate. These exploratory methods may include PK/PD modeling to describe the impact of drug concentration on the inhibition of immunoglobulin production. The decision to perform this analysis will be made by the Sponsor and may require a SAP addendum.

4.3.10 Anti-drug Antibody (ADA) Response Analysis

For cohort 5, if number of either Japanese subjects or non-Japanese subjects is less than 3, cohort 5 won't be included in "by ethnicity" analysis.

[figure not shown]
Anti-VIS649 ADA evaluations will be listed including the confirmatory assay (positive/negative) and titers [Listing 16.2.10.1]. A “titre specific cut-point” might be used to assess titer, another category, for

PAREXEL International

Statistical Analysis Plan

these subjects that are confirmed positive based on the screening cut-point that are not considered positive for titer, might be included in the listing and be footnoted.

[figure not shown]
A summary table of the ADA response (positive or negative) will be presented, by treatment (cohort 1-4 or pooled placebo or cohort 5 or cohort 5 placebo) and by ethnicity and dose separately, based on the Safety Population [Tables 14.3.8.1 and 14.3.8.2]. In addition, the ADA titers (log10) (n, median, minimum and maximum) will be summarized by treatment (cohort 1-4 or pooled placebo or cohort 5 or cohort 5 placebo) and by ethnicity and treatment - separately for all subjects with a positive confirmatory assay at each time point [Tables 14.3.8.3 and 14.3.8.4], this tabulation will include a summary of the highest titer across all time points for each subject.

Following figures will be created for ADA titers.

- Figure 14.2.3.1: Spaghetti Plot of ADA log10 (titer) Over Time (Safety Population). For each dose separately, spaghetti plot of log10 (titer) vs. time, split in pre-Ab negative and pre-Ab positive population will be generated for subjects.
- Figure 14.2.3.2: Mean ADA log10 (titer) Over Time (Safety Population). For each dose separately, line plot of the mean log10 (titer) vs. time, split in pre-Ab negative and pre-Ab positive population will be generated for dose groups.

PAREXEL International
Statistical Analysis Plan

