6.2.2.1. Anti-drug Antibody Response

The serum samples to measure the presence of ADA will be collected on Days 1, Week 4,8,16 and if required Weeks 20 and 24. The presence or absence of ADA will be determined in the serum samples using validated bioanalytical methods. Blood samples for ADA analysis will be collected up to Week 16 from all subjects. Samples for anti-VIS649 antibody titers and neutralizing capabilities will be drawn according to the Schedule of Assessments [Table 9](#). Further procedures for sample collection, shipment, processing and storage will be described in the Laboratory Manual.

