Cohorts	Number of Subjects	Treatment
Cohort 1	N=7	VIS649 0.5 mg/kg
	N=2	Placebo
Cohort 2	N=7	VIS649 2.0 mg/kg
	N=2	Placebo
Cohort 3	N=7	VIS649 6.0 mg/kg
	N=2	Placebo
Cohort 4	N=7	VIS649 12 mg/kg
	N=2	Placebo
Cohort 5	N=10	VIS649 6.0 mg/kg plus vaccine
	N=5	Placebo plus vaccine

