4.1.5 Pharmacokinetic Variables

Blood samples for the determination of the concentration of VIS649 will be collected on Day 1 (prior to the start of infusion, at the end of infusion (60 minutes) and at 2 hours, 8 hours and 24 hours post end of infusion), Days 3, 7, 14, 28, 42, 56, 70, and 112. For details please refer to the Schedule of Assessments in Table 1.

The following PK parameters will be determined for VIS649 in serum samples following single dose administration:

PAREXEL International
Statistical Analysis Plan

Table 5 Pharmacokinetic Parameters after Single Dose Administration

Parameter	Definition
C_{max}	Maximum serum VIS649 concentration determined directly from the concentration-time profile
T_{max}	Time of maximum serum VIS649 concentration determined directly from the concentration-time profile
AUC_{0-112d}	Area under the concentration-time curve from pre-dose (time 0) to the concentration on day 112
AUC_{0-last}	Area under the concentration-time curve from pre-dose (time 0) to the last quantifiable concentration
AUC_{0-inf}	Area under the concentration-time curve from pre-dose (time 0) extrapolated to infinite time [REDACTED]
$t_{1/2}$	Terminal elimination half life
λ_Z	First-order terminal elimination rate constant [REDACTED] [REDACTED] [REDACTED] [REDACTED]
CL	Clearance [REDACTED]
V_d	Volume of distribution [REDACTED]

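### The ADA response table has no class for a negative result that circulating VIS649 could have masked, so ADA incidence at the highest doses could be understated if the assay's drug tolerance is low

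*SAP*

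**What the plan says.** - **ADA timing.** Protocol 6.2.2.1: serum samples "will be collected on Days 1, Week 4,8,16 and if required Weeks 20 and 24". Weeks 20 and 24 depend on immunoglobulin recovery or on emerging data; Protocol 3.1 names ADA detection as a reason for later follow-up. Under SAP Table 1, footnote 2, one subject outside the normal immunoglobulin range at Week 16 sends the whole cohort to both visits.
- **Drug levels.** SAP 4.1.5 lists PK samples on "Days 3, 7, 14, 28, 42, 56, 70, and 112". Days 28, 56 and 112 are the Week 4, 8 and 16 ADA visits.
- **ADA analysis.** SAP 4.3.10: "A summary table of the ADA response (positive or negative) will be presented, by treatment", on the Safety Population, and again by ethnicity (Tables 14.3.8.1 and 14.3.8.2). Titers are also listed, summarised and plotted, but the summaries are restricted to subjects with a positive confirmatory assay. The possible extra listing category concerns confirmed positives that miss the titer cut-point.
- **Use of ADA status.** SAP 1.2 has the secondary objective "To assess ADA status impact on VIS649 PK parameters". Tables 14.2.6.1.1 to 14.2.6.2.2 split concentrations and PK parameters by an overall subject ADA classification, within treatment.
- **Doses.** SAP Table 2 runs from "VIS649 0.5 mg/kg" to "VIS649 12 mg/kg", with 7 active subjects in each of Cohorts 1 to 4. Cohort 5 is "VIS649 6.0 mg/kg plus vaccine" (10 active), so it does not widen the range.
- **Not in the readable text.** The assay's drug tolerance, the half-life and volume of VIS649, and any rule linking a negative ADA result to the drug level at the same visit.

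**The concern.** Drug in the sample can bind ADA and hide it from the assay once its level passes the assay's drug tolerance. A negative from such a sample does not show that ADA is absent, yet a two-class table counts it as negative. At any given visit higher-dose subjects carry more drug, so unreadable negatives would gather in the higher dose groups, and a lower observed incidence there could be partly an assay effect.

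Two secondary objectives rest on this classification: the characterisation of ADA, and its effect on PK. For the second there is a separate problem within a dose group. Whether a subject is called positive would depend partly on that subject's drug level, which is the outcome being compared.

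**Working it through.** The documents give no figure for ADA incidence, tolerance or power, so there is nothing of the plan's own to reproduce.

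**1. Dose ratio (SAP Table 2).** 12/0.5 = 24; 6/0.5 = 12; 2/0.5 = 4. These become ratios of serum level only if PK is linear. Protocol 5.2 uses zero nonlinearity only as a conservative assumption for safety margins.

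**2. Drug remaining at the ADA visits.** Two sets of assumptions, neither from the documents:

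- *Wide*: one compartment, C(t) = (1000 × dose / V) × 2^(−t/t½), with V 50 to 80 mL/kg and t½ 7 to 28 days. At 12 mg/kg on Day 28 this runs from 12,000/80 × 2^(−28/7) = 9.4 to 12,000/50 × 2^(−28/28) = 120 µg/mL.
- *Narrow*: two compartments, initial volume 43 mL/kg, steady-state volume 75 mL/kg, terminal t½ 14 to 28 days. As a check on its upper Week 16 value of 9, one compartment at 75 mL/kg and 28 days gives 12,000/75 × 2^(−112/28) = 160/16 = 10.

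| VIS649, µg/mL | 12 mg/kg wide | 12 mg/kg narrow | 0.5 mg/kg wide | 0.5 mg/kg narrow |
|---|---|---|---|---|
| Week 4 | 9.4–120 | 32–73 | 0.4–5.0 | 1.3–3.0 |
| Week 8 | 0.6–60 | 8–36 | 0.02–2.5 | 0.3–1.5 |
| Week 16 | 0.002–15 | 0.5–9 | 0.0001–0.6 | 0.02–0.4 |

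**3. Scheduled post-dose samples, out of 3, with drug above an assumed tolerance** (read from the table above):

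| Tolerance, µg/mL | 12 mg/kg wide | 12 mg/kg narrow | 0.5 mg/kg wide | 0.5 mg/kg narrow |
|---|---|---|---|---|
| 1 | 1–3 | 2–3 | 0–2 | 1–2 |
| 5 | 1–3 | 2–3 | 0 | 0 |
| 10 | 0–3 | 1–2 | 0 | 0 |
| 50 | 0–2 | 0–1 | 0 | 0 |
| 100 | 0–1 | 0 | 0 | 0 |

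**4. Subject status.** Suppose a subject is called negative on the last sample. For one who completes Week 16, the Week 16 level decides.

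- At 12 mg/kg, status becomes inconclusive only if tolerance is below about 9 µg/mL (narrow) or 15 µg/mL (upper wide limit).
- At 6 mg/kg (7 + 10 = 17 active) the limits halve to about 4.5 and 7.5.
- If Week 24 is taken, the 12 mg/kg limit falls to 9 × 2^(−56/28) = 2.25 (narrow).
- For a subject last sampled at Week 8 it is higher, up to 36 (narrow).

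These are typical levels; variation between subjects is ignored.

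**5. Effect on a group of 7.** With true ADA rate p and half the positives missed, P(0 of 7) moves from (1 − p)^7 to (1 − p/2)^7.

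| Assumed p | Expected positives, all found → half missed | P(0/7), all found → half missed |
|---|---|---|
| 10% | 0.7 → 0.35 | 48% → 70% |
| 30% | 2.1 → 1.05 | 8% → 32% |
| 50% | 3.5 → 1.75 | 1% → 13% |

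Even with perfect detection, 0/7 leaves an exact 95% upper limit of 1 − 0.025^(1/7) = 41%.

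**6. Direction of the within-dose effect.** Take a hypothetical dose group of 7 in which ADA is detected only when the drug level is below 5.

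- True negatives 20, 20, 20; true positives 4, 8, 8, 8. True difference 20 − 7 = 13. Observed: the only positive is 4, and the negatives average (60 + 24)/6 = 14, so the difference is 10. The association shrinks.
- Change the three missed positives from 8 to 20. True difference 20 − 16 = 4; observed 20 − 4 = 16. The association grows.

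**The case against.** **The rule may be blacked out.** Protocol 8.11 ends in redacted text, figures are missing from SAP 4.3.10, listing titles after 16.2.10.1 are hidden, and the overall subject ADA classification has no readable definition. This stands for the PK-by-ADA tables: a reader cannot say that they lack a rule. It carries less weight for the response table, whose defining sentence is complete and gives two classes.

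**ADA is not reduced to yes or no.** Correct: titers are listed, summarised and plotted. But a masked negative never reaches the titer summaries.

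**Weeks 20 and 24 address the problem.** In part. Slow immunoglobulin recovery is a plausible marker of persisting drug, so cohorts with late drug may be the ones that return. The visits remain conditional and are triggered by cohort, so the chance of late detection may itself differ by dose.

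**The effect on subject-level tables is small.** Also fair. Counting unreadable samples overstates it, because a conclusive Week 16 result settles status under a last-sample rule. That rule would still miss a transient response masked at Weeks 4 and 8.

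**Masking exaggerates the ADA-PK association.** A reader might infer this, but the documents do not support it. The tables are split by dose, so the gap between doses does not bias them, and the example shows distortion in either direction. Many cells may be blank anyway, because SAP 4.3.7 gives no PK-parameter statistics for fewer than three values.

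**Conclusion.** The concern holds as a conditional one. The readable SAP counts a possibly masked negative as negative, and the drug level needed to qualify it is drawn at the same visits. If masking occurs, it falls mainly at the highest doses at Weeks 4 and 8 and lowers the observed incidence there. Under the narrow assumptions it changes the status of 12 mg/kg subjects who complete Week 16 only if tolerance is below about 9 µg/mL (15 at the upper wide limit).

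Two stronger readings go too far. One is that serum levels differ 24-fold: that is the dose ratio, and linear PK is not established. The other is that ADA incidence by dose is biased: this depends on a tolerance that the documents do not give, and at a high tolerance the reported results are unaffected. The readable ADA summaries are descriptive, with no dose-trend test, so at stake is how small counts are read. The change is worth making because it is cheap and makes the negatives defensible.

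**What to change.** In SAP 4.3.10:

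1. Class each sample as positive; negative (same-visit VIS649 at or below the validated drug tolerance of the ADA assay); or inconclusive (negative with VIS649 above it). Placebo negatives are conclusive.
2. Call a subject ADA negative only if no post-dose sample is positive and the last available sample, including Week 20 or 24 where taken, is conclusively negative. A subject with neither a positive nor a conclusive last sample is inconclusive.
3. In Tables 14.3.8.1 and 14.3.8.2, show the inconclusive count per dose, preferably by visit as well. Give incidence with and without inconclusive subjects, and footnote the tolerance.
4. Use the same classes for the overall subject ADA classification in Tables 14.2.6.1.1 to 14.2.6.2.2, unless its redacted definition already does so.
5. State what applies if no VIS649 result exists at Week 20 or 24, since the list in SAP 4.1.5 stops at Day 112. After a single dose, a Week 16 level at or below tolerance can qualify later negatives; otherwise they stay inconclusive.

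The cost is SAP wording and one merge of ADA and PK data, with no extra sampling. The downside is fewer ADA-negative subjects at high dose if tolerance is low. If a rule already exists in redacted text or the assay report, citing it is enough.
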